16.1.2 Urine PD Concentrations and Parameters

Part C:

Urine will be collected during 24-hour collection intervals as defined in the schedules of assessments for the analysis of urine calcium, phosphate, creatinine (to calculate the FECa of calcium and phosphate and renal tubular maximum reabsorption of phosphate/glomerular filtration rate [TMP/GFR]),

and magnesium.

The urine PD variables include

- 24-hour urine calcium (calcium excretion rate) = concentration of urine calcium * volume 24h sample
- 24-hour urine calcium adjusted by creatinine = concentration of urine calcium in the 24h urine/
- 24-hour urine calcium adjusted by body weight ¹ = concentration of urine calcium * volume 24h sample / body weight
- 24-hour urine phosphate (phosphate excretion rate) = concentration of urine phosphate * volume 24h sample
- 24-hour urine cAMP (cAMP excretion rate) = concentration of urine cAMP * volume 24h sample

EDSREP 009 T 01 G Page 26 of 53

Version Date: 26-Aug-2022

- Renal clearance of calcium = Urine Ae₀₋₂₄ / Serum AUC₀₋₂₄ for albumin-corrected calcium, where Ae₀₋₂₄ is the total amount of calcium excreted unchanged into urine from time 0 to 24h
- Renal clearance of phosphate = Urine Ae₀₋₂₄ / Serum AUC₀₋₂₄ for phosphate, where Ae₀₋₂₄ is the total amount of phosphate excreted unchanged into urine from time 0 to 24h
- FECa of calcium $(\%)^2 = 100$ * urine calcium * serum creatinine / (serum calcium * urine creatinine)
- FECa of phosphate $(\%)^3$ = 100 * urine phosphate * serum creatinine / (serum phosphate * urine creatinine)
- Tubular reabsorption of phosphate (TRP) = 1 {(urine phosphate/serum phosphate) × (serum creatinine/urine creatinine)}
- Renal TMP/GFR = TRP × serum phosphate if TRP was ≤0.86; Renal TMP/GFR = 0.3 × TRP/[1 (0.8*TRP)] × serum phosphate
- 24-hour urine magnesium (magnesium excretion rate) = concentration of urine magnesium * volume 24h sample (Only for Part C)

Note 1: for 24-hour urine calcium adjusted by body weight: "body weight" refers to the last measurement of body weight before the start of 24-hour interval of urine collection for each day.

Note 2: for FECa of calcium (%): "serum calcium" refers to the measurement at start of 24-hour interval of urine collection for each day.

Note 3: for FECa of phosphate (%): "serum phosphate" refers to the measurement at start of 24-hour interval of urine collection for each day.

16.1.3 Standard of Care

Part C only:

Standard of care will be evaluated at Baseline, at Day 14, at the end of the main treatment period (Day 28) and after 2 weeks during the extension period.

Variables for Standard of Care includes the following:

- Mean active vitamin D dose
- Mean calcium dose
- Number of patients
 - Taking neither vitamin D nor calcium
 - \circ Taking no vitamin D and \leq 1000 mg/day of calcium
 - o Taking no vitamin D and ≤500 mg/day of calcium
 - Taking no vitamin D
 - Taking no calcium
 - o Taking ≤500 mg/day of calcium
 - o Taking ≤1000 mg/day of calcium

16.1.4 EQ-5D Questionnaire

Part C only:

EQ-5D will be used as a self-administered questionnaire measuring generic health status. The EQ-5D questionnaire has 2 components: health state description (using five-level scale) and evaluation (using a visual analogue scale).

Parameters from EQ-5D questionnaire

- Health state description
 - o Mobility
 - Self-care
 - Usual activities
 - Pain/discomfort

EDSREP 009 T 01 G Page 27 of 53

Protocol: AZP-3601-CLI-001 Version Date: 26-Aug-2022

- o Anxiety/depression
- Health state evaluation
 - Overall health status

16.1.5 SF-36 Questionnaire

Part C only:

Short form health survey 36 (SF-36) will be used as a self-administered questionnaire measuring generic health status.

The SF-36 consists of 8 scaled scores, which are based on the sums of the questions in their section. Each scale is directly transformed into a 0-100 scale on the assumption that each question carries equal weight. The lower the score, the more disability. The higher the score, the greater level of functioning i.e. a score of 0 is equivalent to worst functioning and a score of 100 is equivalent to best functioning. The health domain scales will be transformed to T Scores (refer to "User's Manual for the SF-36v2 Health Survey, 3rd Edition"). The 8 scaled scores will be calculated by PRO CoRe 2.0 Smart Measurement System. Missing data will be dealt with using Missing Data Estimation (MDE). Using MDE, the software applies a value to a scale item rendered missing if at least one of the items in that scale has valid data. A scale receives a "missing" score (".") only if all the items in that scale are missing.

- Parameters from short form health survey 36 (SF-36) questionnaire
 - Vitality
 - Physical functioning
 - Bodily pain
 - General health perceptions
 - Physical role functioning
 - Emotional role functioning
 - Social role functioning
 - Mental health

In addition to display of separate scales, component summaries will be shown:

 Physical Component Summary (PCS), summarizing Physical functioning, Physical role functioning, Bodily pain, and General health perceptions

and

 Mental Component Summary (MCS), summarizing Vitality, Social role functioning, Emotional role functioning, and Mental health

16.1.6 DXA Analysis

Part C only:

Bone mineral density (BMD) and Trabecurlar Bone Score will be assessed by DXA. DXA scans will be conducted using standardized procedures and settings. DXAs image will be read using independent central reading.

- Parameters from DXA Analysis
 - BMD (T Score and Z Score)
 - Trabecular Bone Score

16.2 Pharmacodynamic Evaluation

All individual concentration data for the PD assessments and all PD variables will be listed by subject.

[figure not shown]
EDSREP 009 T 01 G Page 28 of 53

Version Date: 26-Aug-2022

16.2.1 Main PD Analysis

The main PD variables refer to the concentration of serum total calcium, albumin-corrected serum calcium and serum phosphate, as well as to the serum AUC_{0-24} for albumin-corrected calcium. The main PD variables will be summarized and listed in US standard units.

Descriptive statistics (n, arithmetic mean, SD, median, min, and max) summarizing the serum concentration for main PD variables (absolute observed value and change from baseline) will be presented by study part and ______/cohort (for Part C) at each scheduled timepoint/day. Taking potential batch effect into consideration, the change from baseline will be calculated with corresponding baseline per batch if applicable; for different batches, all the assessments (absolute observed value and change from baseline (when possible)) will be presented with corresponding batch information separately. For the daily pre-dose timepoints, if a repeat/retest result is available, then the repeat/retest (Batch R) result will be used for the calculations.

Descriptive statistics (n, arithmetic mean, SD, median, min, and max) will also be used to summarize the serum AUC_{0-24} for albumin-corrected calcium. Change from baseline for that AUC will be listed and summarized, which is defined as area under the serum concentration-time curve from time zero up to 24 hours for change from baseline of albumin-corrected calcium.

In Part A, linear plots of the arithmetic mean serum concentrations of main PD variables (absolute observed value and change from baseline) with SD over all scheduled timepoints will be presented by treatment. In Part B, similar linear plots (absolute observed value and change from baseline) will also be provided for each summary tables of serum concentration as described above and presenting only the 24h profile versus time on Day 1, Day 7 and Day 14 (separately). In part C, similar linear plots will be provided by cohort for the main treatment period and for the extension phase separately.

16.2.2 Exploratory Analysis for other PDs and other Measurements

16.2.2.1 Serum

As to the derived PD serum variables in Part C (serum calcium phosphate product, number of patients within the target range of albumin-corrected serum calcium, number of patients within the normal range of albumin-corrected serum calcium, number of patients within target range of albumin-corrected serum calcium who taking no vitamin D and taking <=500mg of oral calcium, number of patients within normal range of albumin-corrected serum calcium who taking no vitamin D and taking <=500mg of oral calcium) will be summarized descriptively by cohort and timepoint. The corresponding numbers and percentages of patients will be summarized at Baseline, Day 14, and Day 28.

EDSREP 009 T 01 G Page 29 of 53

Version Date: 26-Aug-2022

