Part C will be an open-label MAD study in male or female subjects with HP who are on treatment with oral calcium and active vitamin D to evaluate the safety and tolerability, PK , and PD of AZP-3601. Up to 2 cohorts of approximately 12 patients each are planned for this part of the study.

Part C, Main Treatment Period

The overall study schematic for the Main Treatment Period of Part C, is presented hereafter (for more details, please refer to the Schedule of Assessments – Part C in Table 3):

Prior to the treatment period, there will be an optimization period of up to 8 weeks during which doses of oral calcium and active vitamin D will be adjusted to achieve a baseline target range of albumin-corrected serum calcium (7.8 to 9.0 mg/dL, ie, 1.95 to 2.25 mmol/L) and therefore ensuring a close baseline for all patients.

During this optimization period, any serum 25-hydroxy vitamin D (native vitamin D) and/or magnesium deficiencies will be corrected.

During the treatment period, patients in Part C will receive AZP-3601 for 28 days as daily sc abdominal injections (with rotation of injection sites every dosing day).

Doses of oral calcium and active vitamin D supplements will be carefully reduced during the initial 14 days of treatment while maintaining albumin-corrected serum calcium in the target range (7.8 to 9.0 mg/dL, ie, 1.95 to 2.25 mmol/L). Reductions of both oral calcium and active vitamin D supplements will be performed using a staged approach until the active vitamin D dose can be eliminated and the oral calcium dose can be reduced to or below 500 mg/day (please note that throughout this protocol doses of oral calcium refer to doses of elemental calcium). Based on animal data, serum calcium is expected to increase progressively following repeated administration of AZP-3601 and PD steady state is expected to be observed within the first 5 days of dosing. Staggered reductions of doses of oral calcium and active vitamin D supplements will therefore be performed at near-steady state based on the predose albumin-corrected serum calcium value. It is anticipated to perform reduction of supplements on Day 5, 8, and 11 (Cohort C1). The days of dose reduction of supplements for Cohort C2 have been changed to Days 3, 5 and 8 based on data from Part B and from Part C Cohort C1.

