Serum calcium and phosphate blood samples will also be taken on Day 3 (±1 day), Day 5 (±1 day), Day 8 (±1 day), Day 11 (±1 day), Day 21 (±1 day), and Day 30. In addition, there may be additional and unscheduled checks for serum calcium and phosphate at the discretion of the Investigator. After the last study drug administration, if subjects are not entering the extension period, they will be instructed to resume their prestudy calcium and active vitamin D treatment regimen and doses based on assessments performed on Day 28/ET to Day 30.

Extension Phase

Extension phase will start immediately following Day 28 visit. On Days 29 onwards, patients will continue on the same dose of AZP-3601 as on Day 28, then individual titration of AZP-3601 may start as early as Day 30.

Patients will return to the clinical site for additional visits on Day 56 (±4 day), Day 84/ET (±4 day), and Day 85 (Day 84 + 1 day).

Serum calcium and phosphate blood samples will also be taken on Day 42 (±4 day), Day 70 (±4 day), and Day 86 (Day 84 + 2 days). In addition, there may be additional and unscheduled checks for serum calcium and phosphate at the discretion of the Investigator.

Patients will have their serum calcium/albumin levels measured within 5 days after any adjustment of AZP-3601 or any other time at the discretion of the investigator. The investigator will be free to perform any serum or urine test if needed.

After the last study drug administration, the patients will be instructed to resume their prestudy calcium and active vitamin D treatment regimen and doses based on assessments performed on Day 84 (\pm 4 day) to Day 86 (Day 84 + 2 days).

Follow-up

on Day 37 (±2 days). For patients entering the extension phase, follow-up visit will be on Day 98 (±4 days)

* For each study part, the planned treatment period, day of discharge, and follow-up period may be adapted depending on emerging study results.

Subjects/Patients

: Approximately 24 male or female subjects with HP who are on treatment with oral calcium and active vitamin D

Diagnosis and Main Criteria for Inclusion

	- within the normal range of the laboratory under standard of care
	If historical laboratory analysis (≥12 months) is not available, an additional
	recent concomitant laboratory measurement is required (with a minimum of
	3 weeks testing interval).
	- Requirement for therapy with calcitriol ≥0.25 µg per day or alphacalcidol
	≥0.50 µg per day (both are active vitamin D supplements), and requirement

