5.2 Secondary

•

- To assess the PD response of AZP-3601 on maintenance of serum calcium and phosphate levels within a target range while oral calcium and active vitamin D are progressively reduced, following multiple ascending doses administered by sc injection to patients with HP (Part C, Main Treatment Period)
- To assess the PK of AZP-3601 following single and multiple ascending doses administered by sc injection to patients with HP (Part C)
- To assess the feasibility of individual titration of AZP3601 during a 2-month treatment extension period (Part C, Extension Phase) in patients with HP (ie if individual dosing across a dose range can be implemented in a safe and effective manner and can be maintained throughout the treatment period)

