15.2.2.1 Dose-Proportionality

16.0 Pharmacodynamic and other Analysis

16.1 Pharmacodynamic and other Variables

16.1.1 Serum PD Concentrations and Parameters

Part C:

At the time points defined in the schedules of assessments, blood samples will be taken for the measurements of serum total calcium, serum albumin, albumin-corrected serum calcium, serum phosphate, serum creatinine (to calculate the fractional excretion (FECa) of calcium and phosphate), and endogenous serum PTH(1-84).

Serum PD variables include level/concentration of

- Serum total calcium
- Albumin-corrected serum calcium
 - Albumin-corrected serum calcium (mmol/L) = serum total calcium (mmol/L) + 0.020 (40 serum albumin [g/L])
- Serum phosphate
- Endogenous serum PTH(1-84).

Furthermore, serum AUC_{0-24} for albumin-corrected calcium is a serum PD variable, which is defined as area under the serum concentration-time curve from time zero up to 24 hours for albumin-corrected calcium.

EDSREP 009 T 01 G Page 25 of 53

Version Date: 26-Aug-2022

Part only:

In addition to the PD variables listed above, at the time points defined in the schedules of assessments, blood samples will be taken for the measurements of serum 25-hydroxy vitamin D, serum 1.25-dihydroxy vitamin D, serum magnesium and serum bone turnover biomarkers.

Serum PD variables include level/concentration of

- Serum 1.25-dihydroxy vitamin D
- Serum Magnesium
- Serum bone turnover biomarkers:
 - Serum bone-specific alkaline phosphatase (BSAP)
 - Serum carboxy-terminal telopeptide of type I collagen (s-CTx)
 - Serum procollagen type 1 amino-terminal propeptide (P1NP)
 - o Serum osteocalcin

Part C only:

In addition to the PD variables listed above, the following serum PD variables will be calculated:

- Serum calcium phosphate product
 - Serum calcium phospate product (mg2/dL2) = serum total calcium (mg/dL) * serum phosphate (mg/dL)
- Number of patients within the target range of albumin-corrected serum calcium
- Number of patients within the normal range of albumin-corrected serum calcium
- Number of patients within target range of albumin-corrected serum calcium who taking no vitamin D
 and taking <=500mg of oral calcium
- Number of patients within normal range of albumin-corrected serum calcium who taking no vitamin D and taking <=500mg of oral calcium,

where target range refers to 7.8 to 9.0 mg/dL and normal range refers to 8.3 to 10.6 mg/dL.

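### The in-range calcium counts fall on Days 14 and 28 only, so no planned variable measures maintenance in the target range while supplements are being reduced

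*SAP*

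**What the plan says.** SAP 5.2 sets a secondary objective for the Part C main treatment period: "maintenance of serum calcium and phosphate levels within a target range while oral calcium and active vitamin D are progressively reduced". The protocol synopsis has the same wording.

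SAP 16.1.1 derives four counts of patients. The basic one is "Number of patients within the target range of albumin-corrected serum calcium". The others use the normal range instead, or add the condition of no vitamin D and at most 500 mg of oral calcium. The limits are given there: "where target range refers to 7.8 to 9.0 mg/dL and normal range refers to 8.3 to 10.6 mg/dL".

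SAP 16.2.2.1 says these variables "will be summarized descriptively by cohort and timepoint". It then names the days for the counts: "The corresponding numbers and percentages of patients will be summarized at Baseline, Day 14, and Day 28".

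The protocol synopsis (Part C, Main Treatment Period) names Days 5, 8 and 11 for supplement reduction in Cohort C1. For the second cohort it says: "The days of dose reduction of supplements for Cohort C2 have been changed to Days 3, 5 and 8". The last remaining oral calcium may be removed on Day 17. Patients whose AZP-3601 dose is raised after Day 14 may continue reductions in the second two weeks.

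**The concern.** Maintenance during a reduction in supplements is a statement about each patient's course over several weeks. Two separate cross-sections do not describe it: each says who was in range that day and carries no memory of earlier values.

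The gap matters in this design because the protocol's general guidance is to adjust supplements when calcium leaves 7.8 to 9.0 mg/dL. An excursion on Day 5 or 8 may therefore be corrected before Day 14. Unscheduled checks, a likely follow-up to an excursion, are listed but left out of the summaries (SAP 8.1.5).

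The target-range count also puts values below 7.8 together with values above 9.0 mg/dL. The normal-range count does not separate them, because it excludes 7.8 to 8.3, which is on target.

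**Working it through.** The documents give no formula or planned rate for this variable, so there is no figure to reproduce. The check has two parts.

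**1. The days, side by side**

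| Item | Days | Source |
|---|---|---|
| Post-baseline in-range counts | 14, 28 | SAP 16.2.2.1 |
| Named reductions, C1 | 5, 8, 11 | Protocol synopsis |
| Named reductions, C2 | 3, 5, 8 | Protocol synopsis |
| Possible removal of last oral calcium | 17 | Protocol synopsis |
| Calcium sampled on treatment after Day 1 | 3, 5, 8, 11, 14, 15, 16, 21, 28 | Protocol Table 3 |

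- Count days that are named reduction days: none. The ±1-day windows on Days 3 to 11 reach Day 12 at most.
- Sampling days used for counts: 2 of 9.
- Named reduction days with a scheduled sample: 3, 5, 8 and 11. Day 17 has none; the next sample is Day 21.
- By definition, 12 of 12 could be in range on both count days with no patient in range throughout.

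Table 3 marks supplement adjustment at every visit, including Days 14 and 28, so the comparison concerns the named days only.

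**2. How large the gap could be (illustration)**

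Assumptions not in the documents: each patient is in range at any one visit with probability p, the same at all nine visits, and visits share a latent normal correlation ρ. The probability of being in range at k given visits is

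P(k) = E[Φ((z + √ρ·U)/√(1−ρ))^k], with z = Φ⁻¹(p) and U standard normal.

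The share of patients in range on Days 14 and 28 who have at least one of the other seven values out of range is 1 − P(9)/P(2).

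| p | ρ | P(2) | P(9) | 1 − P(9)/P(2) |
|---|---|---|---|---|
| 0.70 | 0.2 | 0.515 | 0.121 | 77% |
| 0.70 | 0.5 | 0.557 | 0.263 | 53% |
| 0.70 | 0.8 | 0.611 | 0.441 | 28% |
| 0.90 | 0.2 | 0.817 | 0.485 | 41% |
| 0.90 | 0.5 | 0.832 | 0.614 | 26% |
| 0.90 | 0.8 | 0.856 | 0.746 | 13% |

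A beta-binomial model gives the same order of size. At p = 0.80 and correlation 0.3 between the yes/no outcomes, a cohort of 12 has on average 8.3 patients in range on both days and 5.0 on all nine: 1 − 5.0/8.3 = 40%.

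In both models the expected per-patient percentage in range equals p, the same as any one-day percentage. Only the figure for all visits in range must be lower.

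**The case against.** The case for the plan has several good parts.

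- **Much of the course is already reported.** SAP 16.2.1 gives mean, SD, median, minimum and maximum of albumin-corrected calcium by cohort at each scheduled timepoint, with plots. SAP 16.2 lists every individual value. SAP 17.1.1 treats hypocalcemia and hypercalcemia as separate events of special interest. A reader might infer that excursions, or their direction, would be hidden; that is not so. The minimum and maximum do not say how many patients were out of range or whether the same patient was out repeatedly, listings are not a summary, and the event tables count reported events rather than values outside 7.8 to 9.0 mg/dL.
- **The count days have a reason.** Day 14 decides the study-drug increase and Day 28 ends the period. The standard-of-care counts use the same main-period days, and two of the four in-range counts need supplement status. This supports keeping these days, not stopping at them.
- **The study is exploratory.** No hypothesis is tested, and the SAP defines no responder. A reader might say that such patients count as successes, but the SAP makes no such claim. Descriptive tables should still describe the stated objective.
- **A count over all visits has limits.** Reductions are based on the predose value, so a sample on the first reduction day precedes any scheduled reduction. Out-of-range values are also the general trigger for adjustment, so the scheme expects some. Both points stand and shape the fix.

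The phrase about cohort and timepoint in SAP 16.2.2.1 could be read as covering every day, but the next sentence names three. The table shells, which might show more, are not in the text reviewed.

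**Conclusion.** The point holds in a limited form. The in-range counts leave out every named reduction day, use two of nine on-treatment sampling days after Day 1, and have no per-patient element. They therefore do not address maintenance during supplement reduction. What is missing is the number of patients out of range on the other days and the number of visits at which each was out.

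The 13% to 77% rests on assumed rates and correlations and on equal rates across visits; it shows that the gap may be large, not what it will be. It would be tempting to conclude that Days 14 and 28 will look better than the course patients actually had. Nothing in the documents shows that calcium control is better on those days than during the reductions, and a model with equal rates cannot show it. Among patients with complete data, the share in range throughout cannot exceed either one-day share. The mean per-patient percentage may be lower, equal or higher.

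**What to change.** In SAP 16.2.2.1, keep the Day 14 and Day 28 counts and add three items for the main period:

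- **(a) By-day counts.** Number and percentage of patients by cohort on every scheduled day, in four classes of albumin-corrected calcium: <7.8, 7.8–9.0, >9.0–10.6 and >10.6 mg/dL. All cut-points are already in SAP 16.1.1.
- **(b) Per-patient percentage.** For each patient, the percentage of scheduled predose values within 7.8–9.0 mg/dL, from the first scheduled sample after the cohort's first reduction day up to Day 28. On the protocol's days that is Day 8 in C1 and Day 5 in C2. Summarise by cohort up to Day 14 (C1: Days 8, 11, 14; C2: Days 5, 8, 11, 14) and for Days 15–28 (Days 15, 16, 21, 28).
- **(c) Supportive count.** The number of patients with all such values in range, with a note that out-of-range values are the general trigger for supplement adjustment.

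SAP 6.0 still gives Days 5, 8 and 11 without distinguishing the cohorts. It must be reconciled with the protocol before the start days in (b) are fixed.

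The cost is SAP wording and one table. No visit or sample is added. The drawback is that the figure in (c) will look less favourable than the one-day counts.
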